| CHMP | Committee for Medicinal Products for Human Use (EMA) |
| CI | confidence interval |
| DVT | deep vein thrombosis |
| EC | ethics committee |
| EDC | electronic data capture |
| EMA | European Medicines Agency |
| ENCePP | European Network of Centres of Pharmacoepidemiology and Pharmacovigilance |
| HCP | health care professional |
| HR | hazard ratio |
| INR | international normalised ratio |
| IRB | institutional review board |
| ITT | intention to treat |
| PE | pulmonary embolism |
| PVCH | BHC pharmacovigilance country head |
| RTI-HS | RTI Health Solutions |
| SPAF | stroke prevention in atrial fibrillation |
| TTR | time in target INR range of 2.0–3.0 |
| UAT | user acceptance testing |
| UK | United Kingdom |
| US | United States |

1 BACKGROUND

Xarelto[®] (rivaroxaban) is a highly selective direct Factor Xa inhibitor with oral bioavailability. Inhibition of Factor Xa interrupts the intrinsic and extrinsic pathway of the blood coagulation cascade, inhibiting both thrombin formation and development of thrombi. Rivaroxaban does not inhibit thrombin (activated Factor II), and no effects on platelets have been demonstrated. It does not require routine coagulation monitoring and has no food interactions and only a few drug interactions compared to standard of care (Xarelto Summary of Product Characteristics—EU, 2011).

Rivaroxaban is currently indicated for the prevention of venous thromboembolism in adult patients undergoing elective hip or knee replacement surgery. Rivaroxaban has recently received a positive opinion by the European Committee for Medicinal Products for Human Use (CHMP) for the prevention of stroke and systemic embolism in adult patients with non-valvular atrial fibrillation (AF) and treatment of deep vein thrombosis (DVT), and for prevention of recurrent DVT and pulmonary embolism (PE) following an acute DVT in adults (Xarelto Summary of Product Characteristics—EU, 2011.)

Atrial fibrillation is the most common cardiac arrhythmia of clinical significance and is an important independent risk factor for cardiogenic thromboembolic events. The prevalence of AF increases with age, being less than 1% among people under 60 years of age, with estimates of more than 6% among those over 80 years of age (Feinberg et al., 1995). AF is estimated to affect over 6 million patients in Europe and approximately 2.3 million in the United States (US), and the number of patients with AF continues to grow in the ageing population (Kannel and Benjamin, 2008). AF is associated with a four- to five-fold increased risk of ischemic stroke (Wolf et al., 1991) and accounts for up to 15% of all strokes and 30% of strokes in patients over the age of 80 (Wolf et al., 1987). In addition, there is evidence that AF-associated stroke is more disabling than non-AF-associated stroke (Jorgensen et al., 1996).

Acute venous thromboembolism (i.e., DVT or PE) is a common disorder with an annual incidence of approximately 1 or 2 cases per 1,000 persons in the general population and is the third most common cause of vascular death, after myocardial infarction and stroke. The current standard treatment for DVT is overlapping parenteral anticoagulation (i.e., low-molecular-weight heparin) and a vitamin K antagonist (i.e., warfarin). Parenteral anticoagulation needs to be continued for 5 to 7 days, at least until an international normalised ratio (INR) of 2.0 has been obtained, followed by a minimum of 3 months of treatment with the vitamin K antagonist. Treatment with vitamin K antagonists requires frequent monitoring of the INR, and multiple interactions of vitamin K antagonists with

foods and other drugs have been reported. The duration of treatment is determined by individual risk factors of the patient.

Two clinical programmes were undertaken to evaluate the efficacy and safety of rivaroxaban in the expanded indications.

1. The ROCKET AF study (Rivaroxaban Once Daily Oral Direct Factor Xa Inhibition Compared with Vitamin K Antagonist for the Prevention of Stroke and Embolism Trial in Atrial Fibrillation) was conducted to evaluate the efficacy and safety of rivaroxaban compared with the vitamin K antagonist warfarin in the prevention of thromboembolic events in patients with non-valvular AF. In the pivotal double-blind study, 14,264 patients were assigned to either Xarelto 20 mg once daily (15 mg once daily in patients with creatinine clearance 30-49 mL/min) or warfarin titrated to a target INR of 2.5 (therapeutic range, 2.0 to 3.0). The median time on treatment was 19 months, and overall treatment duration was up to 41 months. Overall, 34.9% of patients were treated with acetylsalicylic acid, and 11.4% were treated with a class III antiarrhythmic, including amiodarone.

Xarelto was non-inferior to warfarin for the primary composite endpoint of stroke and non-central nervous system systemic embolism (Kannel and Benjamin, 2008; Wolf et al., 1991). In the per-protocol population on treatment, stroke or systemic embolism occurred in 188 patients on rivaroxaban (1.71% per year) and 241 on warfarin (2.16% per year) (hazard ratio [HR], 0.79; 95% confidence interval [CI], 0.66–0.96; $P < 0.001$ for non-inferiority). Among all randomised patients analysed according to intention to treat (ITT), primary events occurred in 269 on rivaroxaban (2.12% per year) and 306 on warfarin (2.42% per year) (HR, 0.88; 95% CI, 0.74–1.03; $P < 0.001$ for non-inferiority; $P = 0.117$ for superiority). Among patients in the warfarin group, INR values were within the therapeutic range (2.0–3.0) a mean of 55% of the time (median, 58%; interquartile range, 43–71). The effect of rivaroxaban did not differ across the level of centre TTR (time in target INR range of 2.0–3.0) in the equally sized quartiles ($P = 0.74$ for interaction). Within the highest quartile according to centre, the hazard ratio with rivaroxaban versus warfarin was 0.74 (95% CI, 0.49–1.12). The incidence rates for the principal safety outcome (major and non-major clinically relevant bleeding events) were similar for both treatment groups.

2. The EINSTEIN clinical trial programme was designed to evaluate the use of rivaroxaban for the acute treatment and secondary prevention of DVT (EINSTEIN-DVT) and PE (EINSTEIN-PE) and in long-term secondary prevention of recurrent DVT and PE (EINSTEIN-EXT). A unique aspect of the EINSTEIN-DVT and PE studies is the use of rivaroxaban as a single agent (single drug approach) in contrast to the use of intravenous anticoagulants and vitamin K antagonists.

The EINSTEIN-DVT study demonstrated that rivaroxaban is at least as effective as the current standard therapy, with similar safety, in the treatment and secondary prevention of DVT. EINSTEIN-EXT demonstrated that continued treatment with rivaroxaban 6 or 12 months after initial treatment is superior to placebo in preventing recurrences and has an acceptable risk of bleeding.

As a result of these programmes, Bayer HealthCare (BHC) pursued indications for the following:

- Prevention of stroke and systemic embolism in adult patients with non-valvular atrial fibrillation with one or more risk factors, such as congestive heart failure, hypertension, aged ≥ 75 years, diabetes mellitus, and prior stroke or transient ischaemic attack.
- Treatment of DVT and prevention of recurrent DVT and PE following an acute DVT in adults.

As a part of this safety risk management plan revision, a physician educational pack has been developed that includes the summary of product characteristics, prescriber guide (Appendix A), and patient alert card (Appendix B), with the aim to increase awareness and understanding among physicians and patients about the potential bleeding risk during treatment with rivaroxaban.

The prescriber guide covers the following topics:

- Switching from or to rivaroxaban treatment
- Necessity of taking the 15-mg and 20-mg tablets with food
- Management of overdose situations
- Use of coagulation tests and their interpretation
- Dosing recommendations
- Perioperative management
- Populations at higher risk of bleeding
- Necessity of providing all patients with a patient alert card and counselling about the details of the patient alert card

The patient alert card contains the following key safety messages:

- Signs or symptoms of bleeding and when to seek attention from a health care provider
- Importance of treatment compliance
- Necessity of taking the 15-mg and 20-mg tablets with food
- Necessity of carrying the patient alert card with them at all times
- Necessity of informing health care professionals (HCPs) that they are taking rivaroxaban if they need to have any surgery or invasive procedure

This protocol describes the planned evaluation of these elements of the risk management plan. Evaluations are planned for administration at 18 months, 3 years, and 7 years post-launch. The status of these assessments will be presented regularly in periodic safety update reports. The five countries to be included in the study are the United Kingdom (UK), Germany, France, Italy, and Spain. Due to drug approval delays in Italy, the 18-month assessment will not include Italy. Therefore, data will be collected from four countries in the 18-month assessment (UK, Germany, France, and Spain).

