2 SPECIFIC AIMS

The primary objective of this cross-sectional epidemiologic study is to measure physician and patient awareness and understanding of the key messages in the prescriber guide and patient alert card.

Specifically, the following objectives will be addressed:

- Investigate whether physicians and their patients have received the educational materials.
- Assess knowledge and understanding among physicians regarding key safety information contained in the prescriber guide and assess how physicians use the materials in their daily practice.
- Assess knowledge and understanding of patients regarding the key safety information contained in the patient alert card and determine if the patients use and carry the patient alert card with them.

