3.1.2 Physician Population and Eligibility

This cross-sectional study will be conducted in each of the five countries (the UK, Germany, France, Italy, and Spain) with distribution among a variety of physician specialties including, for example, general practitioners, cardiologists (office and hospital), haematologists, hospital stroke physicians, emergency care physicians, phlebologists, neurologists, angiologists, and other specialists in internal medicine (office and hospital). Representation by each physician group will reflect, to the extent possible, prescribing patterns in each country. Physicians will complete an online questionnaire eliciting information about their knowledge and use of the prescriber guide for rivaroxaban.

Physicians will be eligible to participate in this study provided they have prescribed rivaroxaban to at least one patient in the past 6 months for one of the following indications:

- Prevention of stroke and systemic embolism in adult patients with non-valvular atrial fibrillation (SPAF).
- Treatment of DVT and prevention of recurrent DVT and PE following an acute DVT in adults.

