3.1.3 Physician Selection and Recruitment

The physician sampling frame will be constructed from a physician panel and/or prescriber list. The final frame will be determined with the objective of achieving a generally representative sample of physicians prescribing rivaroxaban. Geographic location, speciality, practice size, practice type, etc. will be taken into consideration. If the distribution of

physicians in the sampling frame appears consistent with the distribution believed in the targeted population, physicians will be randomly selected from the sample frame. However, if the distributions do not appear consistent with the targeted population, the sampling frame will be stratified by speciality and/or geography, and specific numbers of physicians within each stratum will be selected in order to recruit a sample that matches the distribution in the target population. In this case, the physician recruitment within each stratum will be done randomly. The final sampling strategy will be determined once rivaroxaban is on the market and will be designed to minimise bias and to allow for the study results to be generalised to the entire population of rivaroxaban prescribers to the extent feasible.

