3.2.2 Patient Population and Eligibility

Patients will be identified through selection of a diverse set of medical practices across the five targeted countries. To be eligible for the study, the patients must meet all of the following criteria:

- Patient has taken rivaroxaban within the last 3 months for prevention of stroke and systemic embolism in adult patients with non-valvular atrial fibrillation (SPAF) or

treatment of DVT and prevention of recurrent DVT and pulmonary embolism (PE) following an acute DVT in adults.

- Patient is aged 18 years or older.
- Patient is able to understand and complete the consent form and patient questionnaire.
- Patient can read and understand the native language of the country in which the study is being conducted.
- Patient has not participated in a clinical trial for a treatment to prevent blood clots in the past 12 months.

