Xarelto 15mg and 20mg must be taken with food to ensure sufficient absorption of the drug. The intake of these doses with food at the same time supports the required absorption of the drug, thus ensuring a high oral bioavailability.

Note: Xarelto is also available at a 10mg dose for the prevention of venous thromboembolism (VTE) in adult patients undergoing elective hip or knee replacement surgery. This dose can be taken with or without food.

Dosing in patients with AF

The recommended dose for prevention of stroke and systemic embolism in patients with non-valvular AF is 20mg once daily.

*In patients with moderate or severe renal impairment the recommended dose is 15mg once daily.

Patients with renal impairment:

In patients with moderate (creatinine clearance 30-49 ml/min) or severe (15-29 ml/min) renal impairment the recommended dose is 15mg once daily. Xarelto is to be used with caution in patients with severe renal impairment as limited clinical data indicates a significantly increased plasma concentration. Use is not recommended in patients with creatinine clearance $<$ 15 ml/min.

Duration of therapy:

Xarelto should be continued long term provided the benefit of stroke prevention therapy outweighs the potential risk of bleeding. Clinical surveillance in line with anticoagulation practice is recommended throughout the treatment period.

[figure not shown]

Missed dose:

If a dose is missed the patient should take Xarelto immediately and continue on the following day with the once daily intake as recommended. The dose should not be doubled within the same day to make up for a missed dose.

Dosing in treatment of DVT and PE, and prevention of recurrent DVT and PE in adults

Patients are initially treated with 15mg **twice daily** for the first three weeks. This initial treatment is followed by 20mg **once daily** for the continued treatment period.

* Patients with DVT/PE and renal impairment

Patients with renal impairment

Patients with moderate (creatinine clearance 30-49 ml/min) or severe (15-29 ml/min) renal impairment treated for acute DVT, acute PE and prevention of recurrent DVT and PE do not require a dose reduction.

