In order to continue to monitor and evaluate the safety of Bayer products, the sponsor is interested in any adverse events that have not already been reported. If you have any such adverse events to report for your patients, please do so using the contact information provided here.

[Contact information will be inserted in the survey or on the contact page.]

If you would like additional information or have any questions about the prescribing guidelines or safety information related to Xarelto, please click to the link below to access the Xarelto Prescriber Guide.

[INSERT LINK]

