Appendix D.

Patient Questionnaire

**Xarelto Risk Minimization Study
Survey Instructions**

Thank you for agreeing to participate in this study!

Taking part in this study will take approximately 20 to 25 minutes of your time. Your responses will be kept completely confidential and will not be shared with your health care professionals (e.g., surgery or hospital based doctor or nurse).

This survey consists of two questionnaires. Please follow the instructions below to complete the survey. If you have any questions, please ask the study coordinator for help.

Step 1 - Open envelope #1 and complete the first questionnaire. Please do not refer to the Xarelto patient alert card or other Xarelto educational materials while answering the questionnaire.

Step 2 – When you have completed the first questionnaire, place it back into the envelope and seal the envelope.

Step 3 – Open envelope #2. Inside the envelope you will find a Xarelto patient alert card. Please read the Xarelto patient alert card. After you have read it, complete the second questionnaire.

Step 4 - When you have completed the second questionnaire, place it back into the envelope and seal the envelope.

Step 5 – Return both envelopes to the study coordinator.

**Xarelto Risk Minimization Study
Patient Questionnaire #1**

This is the first of two questionnaires. Please complete this questionnaire before moving on to the second questionnaire (found in a separate envelope).

Please answer the following questions first to confirm that you are eligible for this study.

S1. Are you 18 years of age or older?

- Yes
- No (If no, please speak with the study coordinator to confirm your eligibility.)

S2. Have you taken Xarelto (also known as rivaroxaban) in the past 3 months?

- Yes, I have taken Xarelto in the past 3 months
- No, I have not taken Xarelto in the past 3 months
- I don't know

The purpose of this study is to learn more about your knowledge and understanding of the safety information related to Xarelto (rivaroxaban).

Please do not look at the Xarelto patient alert card while answering the following questions.

Q1. Are you currently taking Xarelto?

- Yes
- No
- I don't know

Q2. Approximately how long have you been taking Xarelto?

Select the one answer that best applies to you.

- Less than 1 month
- Between 1 and 6 months
- More than 6 months but less than 1 year
- More than 1 year
- I don't know

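### Earlier participants are neither excluded nor identified at the 3-year and 7-year waves, so later receipt and knowledge estimates may be biased upward by an unknown amount

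*Protocol*

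**What the plan says.** Section 1 sets out repeated fielding: "Evaluations are planned for administration at 18 months, 3 years, and 7 years post-launch". Italy is left out of the 18-month wave. Section 2 calls the study cross-sectional ("The primary objective of this cross-sectional epidemiologic study is to measure physician and patient awareness and understanding of the key messages"), and the first listed objective is whether physicians and patients received the materials.

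Eligibility does not refer to earlier waves:

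- Physicians (3.1.2), with either indication counting: "Physicians will be eligible to participate in this study provided they have prescribed rivaroxaban to at least one patient in the past 6 months".
- Patients (3.2.2): the only participation bar is "Patient has not participated in a clinical trial for a treatment to prevent blood clots in the past 12 months". That does not cover an earlier round of this survey.
- Sections 3.2.1 and 3.2.3 keep patient-assessment physicians out of the physician assessment, with no reference to waves.
- Section 3.1.3 draws physicians from a panel and/or prescriber list and adds that "The final sampling strategy will be determined once rivaroxaban is on the market".

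The study also exposes its participants to the materials. Of the second patient envelope, Appendix D says: "Inside the envelope you will find a Xarelto patient alert card". The patient reads the card and then answers Questionnaire 2. After the last physician question, Appendix C offers an optional route to the guide: "please click to the link below to access the Xarelto Prescriber Guide".

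Neither questionnaire asks about earlier participation. Patient Q10 asks about receipt of the card at any time before that day. Physician Q19 lists the Prescriber Guide as a source. Neither item sets aside material supplied by the study.

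**The concern.** The receipt objective concerns routine distribution. A patient who took part at 18 months and returns at 3 years can truthfully say that a card had been given before, even if the study was the only supplier. A physician who followed the link can likewise tick the Prescriber Guide. Earlier exposure to the items and the card may also raise knowledge scores. Each effect pushes upward and would make the educational programme look better than it is. A larger sample would not reduce the error, and no confidence interval would show it.

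Some overlap is plausible on the protocol's own facts. Physicians come from a panel or list. Practices must have enough eligible patients, suitable space and a research coordinator (3.2.3), which favours sites already used. In atrial fibrillation the Prescriber Guide says that "Xarelto should be continued long term provided the benefit of stroke prevention therapy outweighs the potential risk of bleeding". The first two waves are 18 months apart (36 − 18), and the atrial fibrillation trial described in Section 1 had a median of 19 months on treatment and a maximum of 41.

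**Working it through.** **1. The plan's own precision.** Exact (Clopper-Pearson) limits reproduce all 8 rows of Table 1, for example 83.1% to 86.8% for 1,500 physicians at 85%. Wald limits with a design effect D of 1, 2 or 4 reproduce all 18 rows of Table 2. These figures are not in dispute and serve as the yardstick:

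- 500 patients at 50%: 1.96 × √(0.5 × 0.5 × D / 500) = 4.4 points (D = 1, ICC 0), 6.2 points (D = 2, ICC 0.11), 8.8 points (D = 4, ICC 0.33).
- 1,500 physicians: 1.96 × √(0.85 × 0.15 / 1,500) = 1.8 points at 85%; 1.96 × √(0.5 × 0.5 / 1,500) = 2.5 points at 50%.

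**2. Bias formula.** Let p be the true percentage without carry-over, f the share of a later sample that took part before, and L the share of those otherwise answering no or wrongly whom earlier participation turned to yes or correct. Assume repeat participants would otherwise have the same p. The expected estimate is (1 − f)p + f[p + L(1 − p)] = p + fL(1 − p), so

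bias = f × L × (1 − p).

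**3. Results in percentage points.** Neither f nor L is in the protocol; all values are assumed.

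| p | f | L = 0.25 | L = 0.5 | L = 1 |
|---|---|---|---|---|
| 50% | 2% | 0.25 | 0.5 | 1.0 |
| 50% | 10% | 1.25 | 2.5 | 5.0 |
| 50% | 20% | 2.5 | 5.0 | 10.0 |
| 85% | 2% | 0.08 | 0.15 | 0.3 |
| 85% | 10% | 0.38 | 0.75 | 1.5 |
| 85% | 20% | 0.75 | 1.5 | 3.0 |

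**4. Overlap at which bias equals the half-width.** f = half-width / [L(1 − p)]. With L = 1:

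- 1,500 physicians: 2.53 / 50 = 5.1% at p = 50%; 1.807 / 15 = 12.0% at p = 85%.
- 500 patients at p = 50%: 4.38 / 50 = 8.8% with ICC 0; 8.77 / 50 = 17.5% with ICC 0.33.

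These shares double at L = 0.5.

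**5. How large physician overlap could be.** If 300 physicians per country were redrawn at random from a frame of N (assumed), overlap after one earlier wave is 300/N: 30% at N = 1,000, 10% at 3,000 and 3% at 10,000. After two earlier waves it is 1 − (1 − 300/N)²: 51%, 19% and 5.9%. The range follows wholly from the assumed N. Patients need more to coincide: the practice chosen again, use within the last 3 months, and selection again.

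**6. What limits the effect.**

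- Patient Questionnaire 1 Q2 records time on treatment, sites supply treatment duration (3.5.3), and Section 5 names stratification of knowledge by duration of use. With waves about 18 months and then 4 years apart, a patient treated for under 1 year cannot have been in an earlier wave, unless treatment was stopped and restarted.
- Nothing collected from physicians plays this role.
- Italy has no 18-month wave, so its 3-year wave cannot carry over. If the other four countries had 10% patient overlap, the pooled 3-year figure would be 10% × 400/500 = 8%, and the bias at p = 50%, L = 1 would be 0.08 × 50 = 4.0 points.

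**The case against.** The strongest reply is that no passage supports any particular overlap or uplift, so the bias could be trivial: at 2% overlap it is at most 1.0 point. One reading of a card may be forgotten over 18 months or 4 years. The protocol is also alert to the study's own influence. Sites are told not to change practice (3.2.6), Section 4 compares recruiting with non-recruiting physicians, and Section 5 lists study-induced education as a limitation. The physician sampling strategy is still open and is meant to minimise bias.

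The point about size stands. The safeguards, however, act only within a wave, and the open sampling strategy covers physicians alone and does not mention waves. Fading applies to knowledge more than to receipt, since a truthful yes to having been given a card can persist.

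A reader might infer several stronger things that the protocol does not support:

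- That later estimates are certainly contaminated. This depends on overlap, which is unknown.
- That physicians are handed the guide or see every item. The link is optional, and Q16 to Q18 are skipped for an indication not prescribed.
- That patients leave with a card. They read it in the session; whether they keep it is not stated.
- That nothing collected could isolate the effect. For patients, treatment duration largely can.
- That uplift could reach 20 points on an item answered correctly by 85%. The ceiling is 15.
- That 4.4 points is the only patient yardstick. With the clustering in Table 2 it is 6.2 to 8.8.

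**Conclusion.** The gap is real: three waves are planned, earlier participation is neither excluded nor recorded in the survey data, and the study exposes participants to the material whose receipt and understanding it measures. Any carry-over would be upward, and patient Q10 and physician Q19 bear on a named objective.

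The supportable conclusion is that later estimates may be biased by an unknown amount. With an assumed 10% overlap and L from 0.25 to 1, this is about 1.3 to 5.0 points at a true 50% and 0.4 to 1.5 points at 85%, and close to nothing if overlap is small. At 10% overlap the patient bias exceeds the half-width only near full conversion and with no clustering. The physician bias at 85% stays below its 1.8-point half-width.

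The matter weighs more for physicians, because patients treated for under a year already give a largely unaffected comparison. That group differs from long-term users, so it serves as a check and not as a replacement estimate.

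**What to change.** Before the 3-year and 7-year waves:

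- Add one prior-participation question to both questionnaires.
- Have the recruiting vendor check earlier panel and practice IDs. This fits Section 3.5.4, under which the research team holds no identities.
- Prefer first-time physicians and new practices where feasible.
- Reword patient Q10 and physician Q19 to exclude materials supplied by this study.
- Where repeat participants are needed to fill a country or speciality, flag them and report receipt and knowledge with and without them, with first-time participants as the main result.

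The cost is one question, two wording changes and an ID check, with a slightly smaller recruitment pool in small specialities. The target sample sizes need not change, and if repeats are fully excluded then f = 0 and the carry-over term disappears. Earlier participation cannot be recovered reliably after a wave has been fielded, so the change has to come first.
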